10.7. Financial other competing interests for the Cl, Pl's, and committee members

Not applicable

10.8. Indemnity

UHD, as sponsor, will be responsible for insurance and indemnity to meet the potential legal liability for harm to participants arising from the management of the research, the design of the research, and the conduct of the research; this is covered under the UHD insurance for clinical trials.

STIM-STROKE Protocol v1.0 30-04-2025

IRAS ID: 332116 Page **62** of **70**

10.9. Amendments

Should a protocol amendment be made that requires REC approval, the changes in the protocol will not be instituted until the amendment and revised informed consent forms and participant and GP information sheets (if appropriate) have been reviewed and received approval / favourable opinion from the REC and R&D departments. A protocol amendment intended to eliminate an apparent immediate hazard to participants may be implemented immediately providing that the REC are notified as soon as possible and an approval is requested. Minor protocol amendments only for logistical or administrative changes may be implemented immediately; and the REC will be informed.

For any amendment to the study, the Chief Investigator, in agreement with the sponsor will submit information to the appropriate body in order for them to issue approval for the amendment. The Chief Investigator will work with sites so they can put the necessary arrangements in place to implement the amendment and to confirm their support for the study as amended. Substantial amendments that require review by NHS REC will not be implemented until that review is in place and HRA approval obtained for the amendment. Access to the final trial dataset

After completion of the trial the final anonymised trial data set will be available upon request (e.g. via BORDAR, Bournemouth Online Research Data Repository).

11. DISSEMINATION POLICY

The findings of this study will be published in academic journals and presented at a national and an international conference. The first publication will be the research protocol. The CI and Project Manager and/or member of the research team will meet with the therapy teams and RNs at the collaborating trusts to share the research and for the teams get familiar with the study.

Annual reports will be sent to the collaborating trusts regarding the progress of the study. We will work with the PAG and public co-applicant to develop a public dissemination strategy including a plain English summary of the study findings and a video/audio version of the study findings.

The findings will be shared in collaboration with the PAG at the at the UK Stroke Forum, through the Stroke Association/local stroke groups, and social media (eg. Twitter). After completion of the study, the team will host an event with the public co-applicant for participants and their families to feed back the findings of the study.

If findings from this feasibility study warrant a full-scale trial we will submit an application to NIHR Health Technology Assessment programme. The findings will help to inform the develop and protocol of a definitive trial to explore if using SNMES on stroke-affected leg muscles in acute and subacute stroke contributes to earlier and improved walking and can slow or prevent muscle atrophy. If it is found that SNMES does contribute to earlier and improved walking and helps to maintain muscle bulk, it will be an intervention for individuals for whom there are currently few interventions early after stroke. Using SNMES in this way could be incorporated into the Stroke Guidelines which would lead to changes in practice and education. Earlier and improved walking would contribute to improved quality of life for people after stroke. Furthermore, if found to be effective this intervention could result in increased therapy time which aligns with the new National Clinical Stroke Guidelines

STIM-STROKE Protocol v1.0 30-04-2025

IRAS ID: 332116 Page **63** of **70**

recommending 3 hours of rehabilitation and 6 hours of activity per day for people following stroke during the recovery phase.

11.1. Authorship eligibility guidelines

Authorship will be determined in accordance with the International Committee of Medical Journal Editors (ICMJE) guidelines, and other contributors will be acknowledged.

13. APPENDICIES

13.1. Appendix 1: Risk

\boxtimes $A \equiv Comparab$ \square $B \equiv Somewhat$	_			
occupational thera has been incorpor guidance IPG278	apy. The use of ele rated into clinical gu "Functional electric	ed as part of standard or usual pracectrical stimulation has been recomruidelines e.g. NICE guidelines such cal stimulation for drop foot of centra Clinical Guideline for Stroke" publish	mended as best pra as Interventional p al neurological origi	rocedures
What are the key therapeutic interveto monitor in this to	entions you plan	How will these risks be minimised	?	
IMP/Intervention	Body system/Hazard	Activity	Frequency	Comment s
Skin irritation at electrode site	Integumentary system	Participant and health care team education on monitoring skin integrity and to report any changes in skin integrity to the research team. The research team will assess the skin integrity and act accordingly to the participants. Hypoallergenic electrodes can be provides if a participant has a skin irritation as well as using a larger electrode.	Healthcare team education session. Initial session of SNMES, check at Visit 2 (week 6) and Visit 3 (week 12)	
Muscle fatigue	Musculoskeletal system	Participant and health care team education on muscle fatigue signs and symptoms. Participants will be instructed to report any muscle fatigue to the research team. The research team will assess the muscle fatigue and act accordingly to the participants symptoms. The intensity of the stimulation can be reduced which will reduce the workload on the muscle.	Healthcare team education session. Initial session of SNMES, check at Visit 2 (week 6) and Visit 3 (week 12)	
Delayed onset muscle	Musculoskeletal system	Participant and health care team education on DOMS signs and symptoms. Participants will be instructed to report any DOMS	Healthcare team education session.	

Page **68** of **70**

STIM-STROKE Protocol v1.0 30-04-2025

IRAS ID: 332116

soreness (DOMS)		to the research team. The research team will assess the DOMS and act accordingly to the participants symptoms. The intensity of the stimulation can be reduced which will reduce the workload on the muscle.	Initial session of SNMES, check at Visit 2 (week 6) and Visit 3 (week 12)
New Joint pain	Musculoskeletal system	Participant and health care team education on joint pain signs and symptoms. Participants will be instructed to report any new joint pain to the research team. The research team will assess the joint pain and act accordingly to the participants symptoms, for example, reducing the intensity of the stimulation.	Healthcare team education session. Initial session of SNMES, check at Visit 2 (week 6) and Visit 3 (week 12)
Pain at stimulation site	Neuromuscular System	Participants and the healthcare team will receive education on recognising signs and symptoms of pain at the site of stimulation. Participants will be instructed to report any pain at the stimulation site to the research team, who will act accordingly to the participants' symptoms. For example, reducing the intensity of the stimulation reducing muscle workload, changing the electrodes, or using larger electrodes.	Healthcare team education session. Initial session of SNMES, check at Visit 2 (week 6) and Visit 3 (week 12)

The research and clinical teams will be educated in the potential risks associated with electrical stimulation as well as how to mitigate the risk and when to refer on for additional assessment or treatment. Participants and their caregivers will also be educated on the potential risks associated with electrical stimulation and instructed to contact a member of the research team as soon as something is not right.

IRAS ID: 332116 Page **69** of **70**

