1.1. Assessment and management of risk

Electrical stimulation is currently being used in routine care physiotherapy practice with minimal reports of adverse events. Electrical stimulation has been incorporated into best practice guidelines for people with stroke as well as people with Multiple Sclerosis. The risk associated with using electrical stimulation within this study is not different to using electrical stimulation within routine clinical practice.

Previous study of electrical stimulation report few adverse events. Common adverse events when they occur are skin irritation at the electrode site, muscle fatigue and soreness following electrical stimulation and joint pain.

Participants will be instructed to let the research team know if they experience any adverse events, these will be monitored as per Section 8 Safety Measures. If participants experience muscle soreness, muscle fatigue, joint pain, or skin irritation they will be supported by the research team to manage this to be able to continue in the study.

The benefits of using electrical stimulation are maintaining muscle bulk and size which will help to prevent atrophy, improved circulation at the stimulation site, and the time doing the stimulation will contribute to additional minutes of exercise which is recommended in the new Clinical Stroke Guidelines.

2. OBJECTIVES AND OUTCOME MEASURES/ENDPOINTS 2.1. Primary objective

The primary aims of this feasibility study are to i. assess the feasibility and acceptability of SNMES started within 2-weeks after stroke and applied for 12-weeks to the weakened lower limb muscles and ii.to provide necessary data to inform the design of a future definitive RCT testing whether SNMES started within two weeks after stroke prevents muscle wastage and improves recovery of strength, walking and quality of life in people with severe lower extremity weakness.

The primary feasibility and acceptability objectives are described below.

- 1. Determine the feasibility and acceptability of the SNMES intervention started within 2-weeks in people after stroke.
- 2. Estimate screening, recruitment and attrition rates, and reasons for declining participation or leaving the study early (where possible).
- 3. Estimate adherence/engagement to the SNMES protocol, including number of sessions completed/total sessions in treatment protocol

STIM-STROKE Protocol v1.0 30-04-2025

IRAS ID: 332116 Page **17** of **70**

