When participants are discharged from the hospital, the stimulator and leg braces will go with them to continue the intervention at home, in rehabilitation, or in a care home. The research assistant will work closely with the rehabilitation teams to track where participants are discharged for seamless continuation with the SNMES protocol, data collection, and return of the stimulator when the intervention is complete. If the participant is discharged to a care home or further rehabilitation, or community rehabilitation, the Project Manager or another member of the research team on the delegation log will orient the respective rehabilitation team to the research study. If the team is outside the trust in which the research is taking place, the staff at the care home or other community teams will also complete the skills competency after training and be added to the delegation log. SNMES protocol, and how to do the SNMES intervention (how to position the electrodes, put on and take off the brace, use the stimulator and seek technical support/trouble shooting). This will help to ensure the intervention can continue after discharge from the hospital.

We will ask participants/caregivers to maintain a treatment diary to track treatment sessions. Participants will log when and where they completed an SNMES session, how they felt during the sessions, any barriers or facilitators to the sessions, and reasons for not completing a session. The treatment diary will be available either in a paper or online format participants' preference, having these options was supported by our PPI work. This will help the team to identify what diary format(s) to use in the definitive trial. Furthermore, the number and duration of sessions recorded in the diary will be cross-checked with data logged by the stimulator.

STIM-STROKE Protocol v1.0 30-04-2025

IRAS ID: 332116 Page **28** of **70**

Control Group

Participants in the control group will continue to receive their usual care. Control group participants will take part in all study assessments. A subgroup of 8 participants from the control group will be invited to take part in an interview at the end of the intervention period to explore their experience of taking part in the study.

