All participants will complete follow up assessments at 6-weeks (Visit 2), 12-weeks (Visit 3) and 6 months (Visit 4) after randomisation. These assessments will be administered by research practitioners and take place at the trust in which the participant was admitted for their stroke (UDH or the second site). If the participant is not able to walk or completes transfers by hoist the assessment can be carried out in the community at their place of residence. Research team members that undertake assessments in the participant's place of residence and will follow lone working policies associated with the trust.

Follow up Assessments

A summary of the study baseline and follow up assessments are in Section 5.5 and 5.6 as well as in Table 2 in Section 5.6.

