6. SAFETY REPORTING

6.1. Definitions

6.1.1. Adverse Event

An AE (Adverse Event) is any untoward medical occurrence in a subject, including occurrences which are not necessarily caused by or related to the study intervention. An AE can therefore be any unfavourable and unintended sign (including an abnormal laboratory finding), symptom or disease temporally associated with study activities.

Examples of adverse events that can occur due to electrical stimulation are:

- Skin redness, irritation, or rash at electrode site or from the brace
- Muscle soreness
- Muscle spasm
- Musculoskeletal injury
- Fatique
- Muscle strain
- Joint paint

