6.5. Responsibilities

Process for SAE

- 1. SAE identified
- 2. SAE CRF completed by a member of the research team
- 3. SAE CRF is sent to the local PI
- 4. Local PI will assess SAE for severity and causality and notify the CI of the SAE
- 5. The Sponsor will be made aware of the SAE within 24 hours of knowledge of the event via a member of the research team

Research practitioner

- Collecting data at study visit (Visit 2, 3, 4) regarding AE, AR, and SAE
- Reporting any AE, AR, SAE on the respective CRF
- Sending SAE CRF to local PI for evaluation

Principal Investigator (PI):

- Checking for SAEs when participants attend the study visit.
- Using medical judgement in assigning seriousness and causality.
- Ensuring that all SUSARs are recorded and reported to the sponsor within 24 hours of becoming aware of the event and provide further follow-up information as soon as available
- Ensuring that SUSARs are chased with Sponsor if a record of receipt is not received within 2 working days of initial reporting.

Chief Investigator (CI):

- Clinical oversight of the safety of study participants, including an on-going review of the risk / benefit.
- Immediate review of all SUSARs.

Sponsor:

- Central data collection and verification of adverse events according to the trial protocol onto a database.
- Using medical judgement to assign the SAE's seriousness and causality where it has not been possible to obtain local medical assessment – UHD Clinical Director for Research.
- Reporting safety information to Research Steering Group.
- Expedited reporting of SUSARs to the REC within required timelines.

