7.3. Statistical analysis plan

Quantitative data

A detailed statistical analysis plan (SAP) will be drafted by the trial statistician and the trial will be reported in accordance with the CONSORT 2010 statement extension to pilot and feasibility trials.⁴⁸

STIM-STROKE Protocol v1.0 30-04-2025

IRAS ID: 332116 Page **54** of **70**

No statistical comparisons between treatment groups will be undertaken on baseline or follow-up data as the trial is not designed to test effectiveness. Iinstead the focus will be on presenting summary statistics with appropriate confidence intervals, to meet listed study objectives.

The flow of participants through the study will be presented in a CONSORT-style diagram with reasons for discontinuation or withdrawal given where available. Descriptive statistics will be reported for the feasibility outcomes: recruitment, retention rate, adherence rates, quality of data collection, intervention delivery and fidelity. Additionally, descriptive statistics will be used to describe the outcome measures collected at Visits 1-4.

Data will inform a potential definitive study with variability in candidate primary and secondary measures calculated to inform size (power calculation) for the definitive trial.

Adverse events will be summarised descriptively.

Data management will be undertaken using REDCap and Microsoft Excel. Statistical analysis will be undertaken using STATA version 16 or later, supplemented where required by R.

Qualitative and quantitative data will be used in combination to inform the future definitive trial design. The intervention and methodology will also be iteratively mapped to the TIDieR checklist, APPEASE framework and Health Inequalities Assessment toolkit.

Qualitative data

Interviews/focus groups will be recorded and transcribed verbatim using an approved transcription service that complies with GDPR. All identifying features of the recording and transcription will be anonymised.

Thematic analysis using the framework method will be used to explore common themes taking a deductive approach and considering emergent themes involving inter-researcher and PPI interpretation ^{44,49} Data management and data analysis may be undertaken using NVivo software.

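### Muscle soreness, fatigue and joint pain have extra detection channels in the SNMES arm only, so descriptive counts of these symptoms by arm will not be like for like (minor, cheap to fix)

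*Protocol*

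**What the plan says.** **Common to both arms.** Section 6.5 gives the research practitioner the task of "Collecting data at study visit (Visit 2, 3, 4) regarding AE, AR, and SAE", without naming an arm. Section 5 states "All participants will complete follow up assessments at 6-weeks (Visit 2), 12-weeks (Visit 3) and 6 months (Visit 4) after randomisation", and of controls that "Control group participants will take part in all study assessments". The definition in 6.1.1 is broad, "including occurrences which are not necessarily caused by or related to the study intervention". Section 1.1 adds a general reporting instruction: "Participants will be instructed to let the research team know if they experience any adverse events". Table 2 in 5.6 schedules a leg pain score at baseline, week 6, week 12 and month 6 for everyone.

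**SNMES arm only.** Appendix 1 (13.1) covers skin irritation at the electrode site, muscle fatigue, delayed-onset soreness, new joint pain and pain at the stimulation site. Each has education on recognising and reporting the problem, and the frequency column reads "Initial session of SNMES, check at Visit 2 (week 6) and Visit 3 (week 12". Section 5 gives SNMES participants a session diary that records, among other things, "how they felt during the sessions".

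**Analysis.** Section 7.3 says "Adverse events will be summarised descriptively" and rules out statistical comparison between the groups.

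**The concern.** Section 2.3 uses adverse events and reactions as part of the evidence on feasibility and acceptability, which is the primary objective. Several of the examples of adverse events in 6.1.1, among them muscle soreness, fatigue and joint pain, are not specific to a stimulator. They are plausible in severely weak stroke patients having usual rehabilitation.

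For such symptoms the control arm supplies the background rate against which the SNMES count will be read. If one arm is taught to recognise a symptom, told to report it, checked for it and given a diary, while the other has visit collection and a general instruction, a higher SNMES count may partly reflect more looking. A symptom never elicited from a control cannot be recovered at analysis, so this belongs in the data-collection rules rather than in a table specification.

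**Working it through.** The protocol gives no figure on this point to reproduce. The check sets the channels side by side, then shows what an ascertainment difference could do.

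**Step 1. Detection channels for a non-device symptom such as soreness**

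| Channel | SNMES | Control | Source |
|---|---|---|---|
| AE/AR/SAE collection at Visits 2, 3, 4 | yes | yes | 6.5 |
| General instruction to report | yes | yes | 1.1 |
| Leg pain score to month 6 | yes | yes | 5.6, Table 2 |
| Hazard education and reporting | yes | none stated | 13.1 |
| Checks at first session, Visits 2 and 3 | yes | none stated | 13.1 |
| Session diary, 3 × 12 = 36 planned sessions | yes | none stated | 5 |

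The first three rows are a common floor. The last three are additional in one arm. A symptom found through them meets the definition in 6.1.1, and nothing in the protocol separates events by how they were found.

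**Step 2. Which hazards are affected.** Electrode-site irritation and stimulation-site pain cannot occur in controls, and cannot newly arise once the stimulators are returned at Visit 3 (trial flow chart). Having no control check and no Visit 4 check for these is no defect. The comparison problem is confined to soreness, fatigue and joint pain.

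**Step 3. Illustrative size.** Six months is 365.25 / 2 / 7 = 26.1 weeks, taken as 26. The extra channels run for 12 weeks, leaving 14. Let *a* be the detection probability with the extra channels and *c* without them. Both are assumptions: *a* = 0.8 to 0.9, *c* = 0.4 to 0.6. With equal and constant true rates:

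ratio = (12*a* + 14*c*) / (26*c*)

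- *a* = 0.8, *c* = 0.6: (9.6 + 8.4) / 15.6 = **1.15**
- *a* = 0.9, *c* = 0.4: (10.8 + 5.6) / 10.4 = **1.58**
- *a* = *c*: ratio = 1, whatever the value

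The simple ratio *a*/*c* (0.8/0.6 = 1.33 to 0.9/0.4 = 2.25) applies only to events in the first 12 weeks. It would describe the whole follow-up only if no events occurred later.

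**Step 4. In counts.** Assume a true expectation of 0.2 events per person for a given symptom, so 30 × 0.2 = 6 per arm.

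- First case: SNMES 6 × 18/26 = 4.2, control 6 × 0.6 = 3.6, difference 0.6.
- Second case: SNMES 6 × 16.4/26 = 3.8, control 6 × 0.4 = 2.4, difference 1.4.

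On these assumptions, the artefact is about one event per symptom in an arm of 30.

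**The case against.** The best reply is that Appendix 1 is a risk-minimisation table, not the adverse-event collection plan. A mitigation schedule for a device naturally follows device users while they use it. The collection rule is in 6.5, and it is the same for both arms at all three follow-up visits. The reply adds that no between-arm test is planned, that adverse events are not among the progression criteria in Table 3, and that the diary is described as a session log cross-checked against stimulator data, with no statement that it feeds adverse-event counts.

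Much of this stands. A reader might infer that reactions are sought only in the SNMES arm and only to week 12, so that the summary differs by arm and period by construction. The text does not support that:

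- Section 6.5 covers both arms to Visit 4, and leg pain is scored in both arms to month 6.
- The protocol does not say whether visit questions are open or prompted, so it cannot be said that controls rely on unprompted recall.
- Section 7.3 does not say that events will be pooled across arms, periods or sources. Table layout, period splits and person-time denominators can be left to the SAP.

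What the reply does not remove is the difference in channels. Soreness found at an Appendix 1 check is an adverse event under 6.1.1 whatever that table's purpose. The absence of a test does not make unequally collected counts comparable, and a descriptive table by arm will still be read across arms.

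**Conclusion.** The asymmetry is real but narrow. General collection is common to both arms. The SNMES arm has additional hazard education, reporting instructions, checks and a diary, with no stated control equivalent. Soreness, fatigue and new joint pain are therefore likely to be detected more often under SNMES. Their descriptive counts by arm are not comparable, and control background rates may be understated.

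The size cannot be taken from the document. The range of about 1.15 to 1.6 over 26 weeks rests on assumed detection probabilities, equal and constant true rates, and the extra channels acting only in weeks 0 to 12. It falls to 1 if detection turns out equal. The point does not threaten the progression decision. It is minor, and worth fixing because the remedy is cheap and must be in place before data are collected.

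**What to change.** In 6.5, state that the visit assessor asks one identical prompted list of non-device symptoms (muscle soreness, fatigue, new joint pain) in both arms at Visits 2, 3 and 4, and that these answers supply any display of those symptoms by arm.

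Report device-specific reactions (electrode-site irritation, stimulation-site pain) for the SNMES arm only. Leave them off the common list: they have no meaning for controls, and asking about them could help unblind assessors whom 5.4 tries to keep blinded. List events found through the diary, SNMES checks or staff separately, by source.

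The cost is a few CRF lines, a source field and about two minutes per visit. The Appendix 1 checks need no change.
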